**1. Introduction and Purpose:**

Propofol has been used in adult populations to treat migraines as an abortive agent. We plan to investigate its efficacy as an abortive agent in the pediatric population when administered as a safe low-dose infusion. Goals of the study are to:

1. Evaluate efficacy of low-dose propofol infusion as an abortive agent in pediatric migraine headaches
2. Evaluate effective and safe dosing limits in pediatric populations
3. Evaluate duration of effect reached from a low-dose propofol infusion as an abortive agent

Endpoints for the study will be:

1. Number of enrolled patients
2. Safety endpoints reached, including: cardiopulmonary depression, excessive somnolence

Risks of the study are minimal due to the use of sub-anesthetic dosing of propofol under the guidance and supervision of a board certified pediatric anesthesiologist with the appropriate monitoring equipment and readily available emergency equipment. We hope to demonstrate more rapid improvement and decreased side-effect as compared to standard care.

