#### *Secondary outcomes:*

- Time to beginning of effect (from the beginning of the propofol infusion till first improvement in pain score noted)
- Duration of effect (from the end of propofol administration till discharge criteria are meet or if treatment is ineffective, till start of new therapy)
- Total propofol dose based on weight.

Goal of subjects to be consented include: 30 to demonstrate effect

Subjects may receive multiple treatments if propofol infusion is effective in reducing headache symptoms.

**Concise Summary:** We will be enrolling subjects who are scheduled to undergo DHE infusion for treatment of migraine headaches as part of standard medical care. Subjects will be identified from the investigators' patient list, of children presenting to the Headache Clinic in the Pain Management Clinic for treatment of migraine headache or who have been admitted to the hospital for treatment of migraine headache. Patients who will be treated at the SPU or during inpatient admission by the DHE protocol will be evaluated for eligibility prior to the visit. If the investigator determines that they would be

eligible, the family will be contacted in advance of the visit to discuss possible participation. An investigator will be present at the visit to discuss the study in further detail and answer any questions, and informed consent will be obtained prior to any study procedures are performed.

Prior to initiation of DHE infusion, the subjects will receive sub-anesthetic doses of propofol infusion: 20 mcg/kg/min for 10 minutes, followed by an increase to 30 mcg/kg/min for 10 minutes and then by an increase to 40 mcg/kg/min for 40 minutes. The propofol infusion will be terminated if:

- The patient has no pain, or greater than 50% reduction in pain scores as compared to the pretreatment pain score
- After completing 40 minutes of propofol infusion at 40 mcg/kg/min irrespective of the pain score
- If the anesthesiologist feels cardio-pulmonary depression, airway obstruction or over sedation (Ramsay Sedation Score greater than 3) has occurred

If the propofol infusion is effective in resolving headache symptoms, then subjects will be monitored for at least 30 minutes after termination of infusion. Outpatient subjects would then be discharged home; inpatient subjects would resume standard care treatment.

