## **METHODS**

### **A. Subject Selection**

#### **a. Inclusion Criteria**

- Patients with a diagnosis of migraine headache per ICHD – 3 (International Classification of Headache Disorders)
- The subjects will have a history of migraine headaches with a presentation consistent with presentations of their headaches in the past with no indication for further investigation for secondary causes of his/her headache.
- Documented pain score greater than or equal to 6 on a 0-10 Numeric Pain Rating Scale.
- Current migraine has a greater than 24 hours duration with a current pain score of 6 or greater on a 0-10 Numeric Pain Rating Scale.
- Subjects will be scheduled for DHE infusion therapy for treatment of migraines per standard medical care
- Patients age 7-18 years old
- Gender: both male and female
- Appropriate fasting interval as per ASA guidelines

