## ETHICAL AND ADMINISTRATIVE SECTION

## **A. Potential patient benefit**

The study aims to show efficacy of a propofol infusion, performed in a controlled and monitored situation with patient safety paramount, will have improved efficacy in providing an abortive therapy for acute migraines in patients refractory to their home regimen. We also aim to show decreased side-effects and sustained headache improvement as compared to DHE infusion. If successful, propofol will be an improvement in treatment and prevent unnecessary emergency center visits and prolonged hospital admission for alternative therapies.

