- Duration of effect (from the end of propofol administration till discharge criteria are meet or if treatment is ineffective, till start of new therapy)
- Total propofol dose based on weight.

Study Endpoints

The propofol infusion was terminated if:

- The patient had no pain, or greater than 50% reduction in pain scores as compared to the pretreatment pain score.
- After completing 40 minutes of propofol infusion at 40 mcg/kg/min irrespective of the pain score
- If the anesthesiologist feels cardio-pulmonary depression, airway obstruction or over sedation (Ramsay Sedation Score greater than 3) had occurred.

STATISTICAL ANALYSIS

Demographic and clinical characteristics for the sample of pediatric patients who received low- dose propofol infusion as an abortive treatment for migraine headaches were described using the sample mean and standard deviation for continuous variables and the frequency and percentage for categorical variables. The mean level of headache pain score at baseline and post-treatment (10-60 minute periods and 24- and 48-hour follow-up) was compared using the dependent samples t-test. Dependent samples t-test was also used to test for differences in the mean percent change in pain severity from baseline to each post-treatment assessment period. Statistical analyses were carried out using SAS software, version 9.4 (SAS Institute, Inc., Cary, NC). The level of significance was set at $\alpha=0.05$ (two-tailed).6.2. Data Analysis General Considerations

Sample Size Considerations

Forty patients were screened, and 38 patients participated in the study.

Handling of Missing Data

Missing data will not be imputed unless otherwise specified elsewhere in this SAP.

Protocol Deviations

Important protocol deviation criteria will be established, and subjects with important protocol deviations will be identified and documented.

Important protocol deviations will be summarized and listed by category for all subjects.

Safety Analyses

All safety analyses will be performed based on the Safety Analysis Set. Descriptive statistics will be used to analyze all safety data.

Adverse Events

Adverse events will be reported during scheduled follow-up communications and documented.

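### The 24 h and 48 h pain scores are compared only with pre-infusion baseline, pooled over all children, so the planned tests cannot show that relief from propofol lasted and can stay significant after most of it is gone

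*SAP*

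**What the plan says.** Goal 3 in Protocol section 1 (Introduction and Purpose) is to "Evaluate duration of effect reached from a low-dose propofol infusion as an abortive agent". Under Potential patient benefit the Protocol also hopes to show "sustained headache improvement as compared to DHE infusion".

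The only endpoint named for duration (Protocol, Secondary outcomes; SAP, Secondary Objectives) runs from the end of propofol to the meeting of discharge criteria or, if treatment fails, to the start of another therapy. It does not reach the follow-up calls at 24 h and 48 h. Those calls record a pain score, side effects and, for children who are not pain-free, when the headache came back (Protocol, item 4, Follow-up).

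The SAP (STATISTICAL ANALYSIS) uses the follow-up scores in two ways. Mean pain at baseline and after treatment ("10-60 minute periods and 24- and 48-hour follow-up) was compared using the dependent samples t-test") is one. A paired test is also used to "test for differences in the mean percent change in pain severity from baseline to each post-treatment assessment period". It names no contrast with a post-infusion reading, no proportion keeping its relief and no analysis of the headache-return item.

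Every child who received an infusion is called. Those with less than 50% reduction go on to DHE (Protocol, Study termination) or, in the SAP overview, to standard of care. Inpatients resume standard care even after a successful infusion.

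**The concern.** The null hypothesis of each follow-up test is that mean pain equals its level before any treatment. Rejecting it shows that some improvement remains on average. It does not show how much of the relief seen in hospital remains, in how many children, or whether propofol produced it.

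The pooled mean adds a second problem. Children who did not respond to propofol and then improved on other treatment lower the 24 h and 48 h means. They can offset responders whose headache returned.

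These tests are the only planned analysis that extends past discharge, so a p-value below 0.05 at 24 h or 48 h is likely to be read as lasting benefit. The data that would answer the question are collected and have no planned use.

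**Working it through.** The documents give no SD, effect size or power for these tests, so there is no planned figure to reproduce.

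**Inputs from the documents**
- Significance: "The level of significance was set at $\alpha=0.05$ (two-tailed").
- Number: "Forty patients were screened, and 38 patients participated in the study" (SAP). The number reached by phone is not given, and missing data are not imputed. The Protocol's target was 30 ("Goal of subjects to be consented include: 30 to demonstrate effect").
- Entry: "Documented pain score greater than or equal to 6 on a 0-10 Numeric Pain Rating Scale".
- Success: complete resolution or a 50% improvement, so at least 3 points from a baseline of 6, or 4 points from a baseline of 8.

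**Assumptions**
- SD of the paired differences: 2 to 4 points.
- Mean initial relief over the children analysed: 3 or 4 points.

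**Step 1. Smallest significant mean drop from baseline** = t(0.975, n−1) × SD/√n.

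For n = 38 this is 2.026/√38 = 0.329 SD, that is 0.66, 0.99 and 1.31 points for SD 2, 3 and 4.

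**Step 2. Share of relief that can be lost before significance ends** = 1 − (smallest significant drop)/(initial mean relief). For n = 38, SD 2 and 3-point relief: 1 − 0.66/3 = 78%.

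| n analysed | Initial relief | SD 2 | SD 3 | SD 4 |
|---|---|---|---|---|
| 38 | 3 points | 78% | 67% | 56% |
| 38 | 4 points | 84% | 75% | 67% |
| 30 | 3 points | 75% | 63% | 50% |
| 30 | 4 points | 81% | 72% | 63% |
| 20 | 3 points | 69% | 53% | 38% |
| 20 | 4 points | 77% | 65% | 53% |

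**Step 3. A check that needs no assumed SD.** Suppose all n children had equal relief, k keep it and the others return exactly to baseline. Then t = √[(n−1)k/(n−k)]. With n = 38 and k = 4, t = √(37 × 4/34) = 2.09, p = 0.044, with 34/38 = 89% of the relief gone. With k = 10, t = √(37 × 10/28) = 3.64, p = 0.0008, with 28/38 = 74% gone. Scatter among the children who relapse would weaken both results.

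**Step 4. The same loss against each comparator.** Take n = 38, 4 points of initial relief and 75% lost, so that 1 point remains, with the same SD for both differences.

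| Comparator | SD 2 | SD 3 | SD 4 |
|---|---|---|---|
| Baseline (1 point below) | p = 0.004 | p = 0.047 | p = 0.13 |
| End of observation (3 points above) | p = 4e-11 | p = 4e-07 | p = 5e-05 |

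The loss is plain against the end of observation. Against baseline, the first two results read as continued benefit.

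**Step 5. Changing the comparator is not enough.** Power to detect a 1-point loss with 38 children is 85%, 52% and 32% for SD 2, 3 and 4. A non-significant loss would therefore not prove that relief was kept, so an estimate with an interval is needed.

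**The case against.** The SAP never calls the follow-up tests a test of durability. They are the last two points of one series that starts at 10 minutes. Baseline is a legitimate reference, because success itself is a percentage of baseline. If the means and percent changes are reported at each time, a reader can see a rebound. All of this stands. What is missing is an estimate of relief retained, child by child, with its uncertainty and free of later treatment.

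The sentence on percent change could be read as comparing periods with one another. It names no such contrast, however, and each change is measured from baseline.

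A reader might infer that the follow-up tests cannot fail, or will stay significant whatever happens. The documents do not support that. The tests fail if pain returns fully to baseline, and they can fail earlier. A remaining drop of 1 point gives p = 0.13 with 38 children and SD 4 (t = 1/(4/√38) = 1.54), or p = 0.09 with 20 children and SD 2.5 (t = 1/(2.5/√20) = 1.79). Non-responders may also pull the initial mean relief below 3 points. At 2 points, n = 38 and SD 4, significance ends at 1 − 1.31/2, about 34% lost.

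The hope of sustained improvement relative to DHE adds little here. There is no DHE control arm, so neither the planned tests nor the fix below can address it.

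A mean change restricted to responders would have its own bias: children selected for a low last score tend to drift upward by regression to the mean.

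**Conclusion.** The concern holds in a limited form. As written, the analysis of the 24 h and 48 h scores can show that mean pain is below its pre-infusion level. It cannot show that relief from propofol was maintained, and the named duration endpoint stops too early to fill the gap.

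With 38 children analysed, a significant result is compatible with a loss of 56% to 78% of a 3-point mean relief, or 67% to 84% of a 4-point relief. These ranges rest on an assumed SD of 2 to 4 points and on the assumed mean relief. They narrow with fewer children reached, to 38% in the least favourable row of the table. The gap in interpretation does not depend on these assumptions.

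Nothing here shows that relief was in fact lost. The point affects a stated study goal, not the in-hospital primary outcome. It should be corrected.

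**What to change.** Add to the SAP, labelled post hoc if results are already known (the SAP is dated December 2023 and describes completed analyses):

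1. **Sustained relief.** The proportion of all infused children who met the success criterion at the last post-infusion study reading and still meet it at 24 h, and at 48 h, without DHE or other new abortive therapy. Give an exact 95% CI; for illustration, 10/38 = 26% (13% to 43%). State the number reached by phone and how children not reached are counted. Show the same proportion among initial responders.
2. **Time to headache return**, from the item collected at the calls, censored at the last contact.
3. **Mean change from the last post-infusion reading** to 24 h and 48 h with 95% CI, as an estimate only. Note regression to the mean if it is restricted to responders.
4. **Baseline comparisons at 24 h and 48 h** kept as descriptive, and not interpreted as evidence of sustained relief or of superiority to DHE.

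The last reading needs a definition. Observation after success is at least 30 minutes in the Protocol's Concise Summary and the SAP overview, but one hour under Study termination, and these passages must be reconciled. The definition should also say how a reduction of exactly 50% counts, since the primary outcome refers to 50% and the stopping rule to more than 50%.

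The cost is SAP wording, a little more analysis of scores already collected, and probably a less favourable durability figure. One limit should be stated: use of other medication at home is not among the listed phone items, so later therapy in outpatients may be incompletely known.

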Four studies in the adult population have shown efficacy with propofol as an abortive agent when it was administered in sub-anesthetic bolus dosing.

Krusz et al, found a 95.4% rate of success in treating intractable headaches in the adult population with propofol. Eighty-two percent of the patients had complete resolution of their headaches. The remaining patients had a 50-90% reduction in their pain scores. At the sub anesthetic propofol dose administered, there was no incidence of loss of consciousness recorded. The total amount of propofol given averaged 110 mg with no weights given for per kg dosing. Mosier et al recently reported a case series of adults presenting to the ED with failed outpatient treatment of migraine headache. Patients were treated with a sedation dose of 1mg/kg of propofol; all subjects reported dramatic improvement or complete resolution of headache symptoms and had a 50% reduction in length of stay as compared to the average LOS for patients with similar chief complaints. No events of hypotension, hypoxia or apnea were reported in these cases (12).

Data about use of propofol as an abortive agent for pediatric patients with migraine is limited. In a retrospective review of seven patients, Sharidan et al (8) found an 80% efficacy rate in reducing intractable headaches with bolus doses of propofol without noting any adverse effects. The total propofol dose administered was 1.71 mg/kg with a range of 0.81 – 3.72 mg/kg. Since this was a small retrospective study, no data was available on the length of the headache relief or the degree of sedation the patients experienced.

As the pathophysiology of migraine headaches remains unknown, the exact mechanism of action of propofol's abortive therapy is also uncertain. The Krusz study  raised questions regarding the GABA system and its mechanism regarding intractable headaches. One possible hypothesis suggested that the GABA system is in a low functional state at the time of the headache. This would lead one to conclude that stimulating the system would lead to resolution of symptoms. Propofol's GABA agonism has been documented. The effects of propofol on the central nervous systems have been well studied, some effects include:

- GABA agonism leading to neuronal hyperpolarization and generalized inhibition of neuronal firing,
- enhanced anti-nociceptive dorsal root potentials, inhibition of sympathetic efferent activity,

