#### *Primary outcome:*

Based on the adult and the limited pediatric data available we hypothesize that propofol infusion in sub anesthetic dose, will result in either complete resolution or improve the headache pain scores by 50% from the baseline pain scores. Patients will be assessed with a 0-10 Numeric Pain Rating Scale.

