Title: Low- Dose Propofol Infusion as an Abortive Treatment for Migraine Headaches in Pediatric Patients

NCT number: NCT02485418

Document date: December 29,2023

INTRODUCTION

The purpose of this statistical analysis plan (SAP) is to describe the procedures and the statistical methods that will be used to analyze and report results for study STU 042014-002 Low- Dose Propofol Infusion as an Abortive Treatment for Migraine Headaches in Pediatric Patients.

STUDY OVERVIEW

The aim of this prospective study was to evaluate the efficacy and safety of propofol administration in a hospital setting, as an abortive medication for children aged 7-18 with migraines.

We enrolled subjects who were scheduled to undergo DHE infusion for treatment of migraine headaches as part of standard medical care. Subjects were identified from the investigators' patient list, of children presenting to the Headache Clinic in the Pain Management Clinic for treatment of migraine headache or who had been admitted to the hospital for treatment of migraine headache. If the investigator determined that they were eligible, the family was contacted in advance of the visit to discuss possible participation. An investigator was present at the visit to discuss the study in further detail and answer any questions, and informed consent was obtained prior to any study procedures performed.

Prior to initiation of DHE infusion, the subjects received sub-anesthetic doses of propofol infusion:

20 mcg/kg/min for 10 minutes, followed by an increase to 30 mcg/kg/min for 10 minutes and then by an increase to 40 mcg/kg/min for 40 minutes.

If the propofol infusion was effective in resolving headache symptoms, then subjects were monitored for at least 30 minutes after termination of infusion. Outpatient subjects were discharged home.

If propofol infusion was not successful in resolving the headache, then the subjects proceeded with standard of care.

For all subjects who received a propofol infusion, follow-up occurred at 24 and 48 hours via phone call to evaluate headache status and recover information on headache symptoms and side effects.

STUDY OBJECTIVES

Primary Objective

Based on the adult and the limited pediatric data available we hypothesized that propofol infusion in sub anesthetic dose, would result in either complete resolution or improvement in headache pain scores by 50% from the baseline pain scores. Patients were assessed with a 0-10 Numeric Pain Rating Scale.

Secondary Objectives

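### The primary hypothesis is pain freedom or a 50% improvement, but the SAP plans only t-tests of mean score and mean percent change, with no responder proportion, confidence interval or 50% reference

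*SAP*

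**What the plan says.** The Protocol (Primary outcome) hypothesises that a sub-anesthetic infusion "will result in either complete resolution or improve the headache pain scores by 50% from the baseline pain scores". The SAP (Primary Objective) repeats this: the infusion "would result in either complete resolution or improvement in headache pain scores by 50% from the baseline pain scores".

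The SAP's Statistical Analysis section gives two efficacy analyses. Mean pain score "at baseline and post-treatment (10-60 minute periods and 24- and 48-hour follow-up) was compared using the dependent samples t-test". The second is on the percent scale: "Dependent samples t-test was also used to test for differences in the mean percent change in pain severity from baseline" to each later assessment. The significance level is 0.05, two-tailed. No null or reference value is given for either test.

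Two other lines in the SAP come near the missing analysis:
- Under Study Endpoints: "The patient had no pain, or greater than 50% reduction in pain scores as compared to the pretreatment pain score". This is the first item in a list of reasons for ending the infusion, and no analysis is attached to it.
- In Statistical Analysis: "the frequency and percentage for categorical variables". The subject of that sentence is demographic and clinical characteristics, not response.

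The Protocol's Biostatistics item only says who will do the analysis.

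**The concern.** The hypothesis sets a threshold and the planned tests do not use it. A paired t-test of change, read in the usual way against zero, asks whether pain fell at all on average. It does not ask how many children became pain-free or halved their score, or whether the average fall reached 50%.

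This matters more than usual because the study has one arm and an entry score of at least 6. Some average fall would be unsurprising, so a small p-value against zero says little about the stated hypothesis. Followed as written, the plan could yield strong significance at effects well short of 50%, with no planned figure to show the shortfall.

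**Working it through.** **The plan's own figure.** The Protocol's target of 30 subjects comes with no effect size, SD, response rate or power, so it cannot be reproduced, and there is no power claim to check. The SAP reports 38 participants, used below.

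**Inputs.** From the documents: n = 38, two-sided α = 0.05, baseline score 6 to 10 (entry requires at least 6 on a 0-10 scale). Assumed, because the documents give none: SD of percent change 25 to 40 points, SD of change 2 to 3 scale points, and a null of zero change.

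**Step 1: smallest significant mean reduction.** This is t(0.975, 37) × SD/√n, with t = 2.026 and √38 = 6.164.
- SD 25: 2.026 × 25/6.164 = 8.2%.
- SD 40: 2.026 × 40/6.164 = 13.1%.

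**Step 2: a 30% mean reduction, which falls short of 50%.** The CI is 30 ± the margin from step 1.
- SD 25: t = 30/4.06 = 7.40, p = 8e-9, 95% CI 21.8% to 38.2%.
- SD 40: t = 30/6.49 = 4.62, p = 4e-5, 95% CI 16.9% to 43.1%.

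Both results are highly significant, yet both intervals exclude 50% from below. This covers the group-mean reading of the hypothesis.

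**Step 3: the patient-level reading.** Take a true mean fall of 1.5 points. Power comes from the noncentral t with noncentrality 1.5 × √38/SD. The share of patients with at least a 50% fall, treating change as continuous and normal, is 1 − Φ((b/2 − 1.5)/SD) for baseline b.
- Power: 99% (SD 2), 95% (SD 2.5), 85% (SD 3).
- Lowest share: b = 10, SD 2, z = 1.75, giving 4%.
- Middle case: b = 8, SD 2.5, z = 1.00, giving 16%.
- Highest share: b = 6, SD 3, z = 0.50, giving 31%.

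So the t-test would very probably succeed while about 4% to 31% of patients respond. With whole-number scores the range is 7% to 37%.

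**Step 4: what the missing analysis would give.** Exact Clopper-Pearson 95% limits are the 0.025 quantile of Beta(x, n−x+1) and the 0.975 quantile of Beta(x+1, n−x). For illustrative counts out of 38:
- 19 (50%): 33% to 67%.
- 23 (61%): 43% to 76%.
- 30 (79%): 63% to 90%.

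**The case against.** The strongest reply is that the SAP has no rule making p<0.05 proof of the hypothesis, and that mean percent change is on the right scale. If the estimate is printed with the test, a reader who sees 19% or 30% can set it beside 50%. The hypothesis can also be read as a statement about the group mean, in which case the SAP has the right variable. This stands in part. The plan is then short only of a confidence interval or a 50% reference, but it is still short of one: the planned p-value does not address 50% on either reading.

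A reader might go further and infer that the plan is likely to declare success when no patient responds. That can be constructed, but it is not a likely outcome. Under the step 3 model at baseline 8, with an SD of 2 to 3, the chance of 0/38 responders is at most (1 − 0.1056)^38 = 1.4%. It rises to (1 − 0.0401)^38 = 21% only if every child starts at 10 and the SD is 2. The fair statement is the 4% to 31% response range. The risk also shrinks as the effect grows: at a true mean fall of 4 points, the share reaching 50% on whole-number scores is 40% to 77%.

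A reader might also infer that a responder rate is needed for direct comparison with the Protocol's Background. The adult series "found a 95.4% rate of success in treating intractable headaches in the adult population with propofol", and the pediatric review "found an 80% efficacy rate in reducing intractable headaches with bolus doses of propofol". But the pediatric figure comes from seven patients with no 50% threshold stated, so the comparison would not clearly be like for like. The Background also gives the DHE evidence as a 60% reduction in severity at one hour, to which mean percent change is closer. The case for a responder proportion therefore rests on the trial's own hypothesis.

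**Conclusion.** The mismatch is real. Neither reading of the primary hypothesis is tested by the planned analyses, and no other line in either document fills the gap. The patient-level reading is the more natural one, given the either/or wording and the use of the same kind of criterion to stop individual infusions.

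The size rests on assumed SDs and baselines and on a null of zero that the SAP does not state. Across those ranges, significance starts at roughly a sixth to a quarter of the hypothesised improvement (8.2/50 = 0.16, 13.1/50 = 0.26).

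This should be fixed, but it does not invalidate the study. The data needed are already scheduled, the study has no formal decision rule to overturn, and the risk of a wrong conclusion is small if the effect is large. The documents do not support a claim that the reported conclusion is or will be wrong.

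**What to change.** - **Main efficacy result.** Report the proportion of treated subjects, first infusion only, who are pain-free or meet the 50% criterion at one stated time, with an exact (Clopper-Pearson) 95% CI. First infusion, because the Protocol allows repeat treatment when propofol has worked. End of infusion is a workable time because it precedes DHE; state that stopping on response favours that score.
- **Secondary times.** Show the same proportion at 60 minutes, 24 hours and 48 hours, with the number assessed at each. State whether 60 minutes runs from the start or the end of infusion.
- **Definition.** Choose 'at least' or 'greater than' 50% and show the other as a sensitivity analysis. A fall from 6 to 3 or from 8 to 4 turns on this.
- **Mean change.** Report mean percent reduction with a 95% CI beside 50%. Keep the t-tests as supportive.
- **Later treatment.** At secondary times, count as non-responders those who went on to DHE because propofol had failed, where this is recorded. Do not count inpatient responders who only resumed standard care as failures, but flag them.
- **Label.** Present the analysis as estimation, specified after enrolment: the SAP is dated December 2023 and already reports 38 participants.

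The cost is SAP wording and one table, mostly from scores the Protocol already schedules. The downsides are that the analysis is post hoc, the interval is wide (23/38 gives 43% to 76%), and rescue data after discharge may be incomplete, since neither the follow-up call list nor the Data Collection list names rescue use. It does not make up for the lack of a control arm.

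The sections that use 50% for stopping and disposition (Protocol, Concise Summary, section B and Study termination; SAP, Study Endpoints) should be reconciled separately. No clinical rule is proposed here.
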